7.3.5. Derivation of Responder Status at Week 24/EOT and Missing Data Handling Rules

For the evaluation of primary endpoint, missing data handling rules will be implemented for deriving responder status at Week 24/EOT as described below. The following elements will be checked: duration of treatment exposure; compliance with feminine product collection against the eDiary, as measured by FP RR; compliance with eDiary entry, defined as the proportion of eDiary entry days over the length (days) of FP collection interval for Week 24/EOT visit; and reasons for no FP collection (as displayed in [Table 7](#)).

Patients with < 4 weeks of treatment who withdraw from the study prematurely due to lack of efficacy or withdraw from the study prematurely to undergo surgical intervention for uterine fibroids will be considered as non-responders.

All other patients will have their responder status determined as follows:

- For patients with a FP RR of 100%, responder status will be determined based on the observed MBL volume;
- For patients who had incomplete feminine product collection, with a FP RR of < 100%, responder status will be derived based on either imputed or observed MBL volume;
 - Those with an MBL volume \geq 80 mL or < 50% reduction from Baseline will be considered as non-responders;
 - Those with an MBL volume < 80 mL and \geq 50% reduction from Baseline will be imputed for partial or complete missing MBL volume (see Section [7.3.6](#) for details).
- For patients who did not return a feminine product collection, responder status will be determined depending on the reason reported on the Feminine Product Collection eCRF:
 - If the reason is reported as Amenorrhea, the last 35 days of treatment will be used to derive responder status:
 - If the Week 24/EOT interval was 35 days, then she will be considered as a responder;
 - If the Week 24/EOT interval was <35 days, the following supportive information will be used to derive responder status:
 - If a patient reported amenorrhea at the visit prior to Week 24/EOT, she will be defined as a responder;
 - If a patient did not report amenorrhea at the visit prior to Week 24/EOT, eDiary data from the prior visit interval will be reviewed to confirm whether the patient was amenorrheic for a total of 35 days.

- If the eDiary from the previous interval confirms amenorrhea, then the patient will be considered as a responder;
- Otherwise, MBL volume will be imputed.

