Abbreviations: eDiary, electronic diary; FP, feminine product; EOT, end of treatment; MBL, menstrual blood loss; N/A, not available.

^a Defined as those patients who meet the following criteria: eDiary entry rate > 70% and no more than 3 consecutive days and no more than 5 days of bleeding/spotting and use of feminine product reported on the eDiary over the Week 24/EOT visit window (see [Table 5](#)).

7.3.6. Mixed-Effects Model for Imputing Missing or Partially Missing MBL Volume at Week 24/EOT

For the primary analysis, patients with missing MBL volumes at Week 24/EOT will be identified per missing data handling rules as described above. For imputing missing data for the primary analysis, a mixed-effects model approach will be used, as the mixed-effects approach may better describe the effects of a hormonal treatment (such as suppression of the hypothalamic-pituitary-ovarian axis by GnRH antagonists).

Specifically, a mixed-effects model with repeated measures of MBL volumes at multiple time points (Weeks 4, 8, 12, 16, 20 and 24) will be fitted to predict percent change in MBL volume from Baseline (as a dependent variable) through the fixed-effects associated with covariates (ie, stratification factors of Baseline MBL volume and geographic region, visit, treatment, and visit by treatment interaction) and random effects (from the individual patients). In this model, an unstructured variance-covariance matrix is assumed for each patient.

See sample SAS codes below for illustration where PCHG_MBL is percent change in MBL volume from Baseline as a dependent variable, PID is patient identification number, BMBL is a randomization stratification factor (Baseline MBL < 225 vs \geq 225), REGION is a randomization stratification factor (North America vs Rest of World), TRT is treatment group (relugolix + E2/NETA or Placebo), VISIT is visit time point (4, 8, 12, 16, 20, and 24 weeks) and TRT*VISIT is the visit by treatment interaction. The specification of type=UN implements unstructured variance-covariance matrix for an individual patient with multiple measures of MBL volumes.

```
proc mixed data=MBL_dataset method=REML covtest;
  class PID BMBL REGION TRT VISIT;
  model PCHG_MBL= BMBL REGION VISIT TRT VISIT*TRT/s outp=ufmi_mixed_p
  covb;
  repeated VISIT /type=UN subject=PID r;
  lsmeans TRT/diff;
  ods output SolutionF=mixparms CovB=mixcovb;
```

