Applying this model over the observed longitudinal MBL volume data, the fixed-effects will be estimated and relationship of percent change in MBL volume from Baseline with the covariates will be characterized by the fitted model. From the fitted model, the percent change in MBL volume (whether missing or not) will be predicted for each patient at each visit and in a particular stratum. The imputed MBL volume will be obtained by first multiplying the imputed percent change with the individual patient's Baseline MBL volume to the difference, and then adding the Baseline BML volume to the difference.

The main reason for using percent change in MBL volume over reported MBL volume as a dependent variable in the mixed-effects model is that the percent change is part of the derivation of the primary endpoint. Secondly, the percent change is a normalized value adjusted for the Baseline value and less influenced by Baseline MBL volume, and therefore it is a better metric to describe the relationship of MBL volume reduction with hormonal treatment and to impute the missing volumes in a more robust fashion.

Statistical Analysis Plan
Amendment 1: Effective June 14, 2019

MVT-601-3001 and 3002

Since the purpose of using a mixed-effects model is imputing the missing MBL volumes identified at Week 24/EOT, the predicted MBL volumes at the corresponding Week 24/EOT visit will be used to determine responder status. For patients without the need for imputation, their responder status will be derived according to the algorithms laid out in [Table 7](#). This imputation approach is consistent with the definition of responder at Week 24/EOT for the primary analysis.

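### Section 7.3.6 does not say that a partial Week 24/EOT volume is set to missing before the imputation model is fitted; if it is kept, treatment arm largely decides responder status in that cell

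*SAP*

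**What the plan says.** The references are to SAP Amendment 1.

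**Who is imputed.** In Section 7.3.5 and Table 7, a woman with a feminine product return rate (FPRR) below 100% whose volume is below 80 mL with at least a 50% reduction "will be imputed for partial or complete missing MBL volume". Her responder status then rests on the imputed volume.

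**The model.** The prose of Section 7.3.6 lists the two stratification factors, visit, treatment and their interaction as fixed effects. It adds "random effects (from the individual patients") and an unstructured covariance matrix. The code is introduced with "See sample SAS codes below for illustration". Its two working lines are "model PCHG_MBL= BMBL REGION VISIT TRT VISIT*TRT/s outp=ufmi_mixed_p" and "repeated VISIT /type=UN subject=PID r". There is no RANDOM statement.

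**Data and prediction.** The text continues with "Applying this model over the observed longitudinal MBL volume data" and then states that "the percent change in MBL volume (whether missing or not) will be predicted for each patient at each visit and in a particular stratum". The predicted percent change is applied to the woman's own Baseline volume. Women who need no imputation follow Table 7 directly.

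**How a partial volume is named.** The heading of Section 7.3.6 calls it partially missing, and Sensitivity Analysis 6 imputes it. Table 7, however, lists it in its column of observed volumes. Sensitivity Analysis 2 likewise uses the observed volume when collection was incomplete.

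**The concern.** One unstated step controls the primary endpoint in this cell. A programmer who treats the partial volume as missing obtains a prediction that uses the woman's own other visits. A programmer who follows the words observed data literally leaves the partial row in and obtains a mean for her arm and strata. Both can claim to have followed Section 7.3.6.

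Under the second reading, a placebo woman with five complete low-volume collections is scored on the placebo mean. A relugolix + E2/NETA woman with five poor collections is scored on the relugolix mean. If the two means lie on opposite sides of the 50% criterion, the errors run in opposite directions and both widen the treatment difference.

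**Working it through.** **1. The plan's own figure.** The SAP gives no figure for the imputation step. Its power statement (Section 2.2.1) is at least 99% with 130 per arm, 20% dropout, and 25% versus 55% responders at two-sided 0.05. With 130 × 0.8 = 104 evaluable per arm, a chi-squared calculation gives 99.5% (99.9% with 130), so the statement reproduces. What is exposed here is mainly the effect estimate, not the test.

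**2. What the code returns.** This is general linear-model algebra and software behaviour, not SAP text. Let Xβ be the fixed-effect mean, V the covariance of the visits with a response, and C the covariance of Week 24 with those visits.
- Response present in the row: prediction = Xβ.
- Response missing in the row, other visits present: prediction = Xβ + C V⁻¹ (y − Xβ), which uses her own other visits.

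The missing RANDOM statement therefore does not by itself remove individual prediction. What matters is whether the row is set to missing.

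**3. Two worked women.** Assumptions: Week 24 means of −84% (relugolix + E2/NETA) and −20% (placebo), equal SDs, a common between-visit correlation ρ, and a deviation of 50 points from the arm mean at all five earlier visits. The adjustment is then 50 × 5ρ/(1 + 4ρ), which is 34.1, 41.7 and 46.1 points for ρ = 0.3, 0.5 and 0.7.

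| Woman | Row kept | Row set to missing (ρ = 0.3 / 0.5 / 0.7) |
|---|---|---|
| Relugolix + E2/NETA, 50 points worse than her arm | −84% | −49.9 / −42.3 / −37.9% |
| Placebo, 50 points better than her arm | −20% | −54.1 / −61.7 / −66.1% |

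Against the 50% criterion, her status flips in every case.

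**4. Role of Baseline.** With predicted change m, the 80 mL criterion needs Baseline < 80/(1 + m/100). At −80% this is 80/0.20 = 400 mL, and at −60% it is 80/0.40 = 200 mL. Baseline can therefore still fail a relugolix woman. It cannot rescue a placebo woman whose predicted reduction is below 50%.

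**5. One simulated trial.** Assumptions: 128 per arm, 20% partial return, half the volume returned, the means in step 3, SD 35, ρ = 0.5, arm-by-visit means without stratum terms, and the 50% criterion only. Every partial Week 24 value was either kept or set to missing.

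| | Relugolix + E2/NETA (n = 22) | Placebo (n = 15) |
|---|---|---|
| Kept: prediction for every woman | −79.3% | −28.3% |
| Kept: meet criterion | 22/22 | 0/15 |
| Set to missing: meet criterion | 95% | 20% |
| Truth | 82% | 40% |

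With the value set to missing, predictions varied between women with an SD of about 15 points. A single trial shows the mechanism, not the size.

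**6. Size on the responder difference.** Simulation of 200,000 women per arm under Table 7. Assumptions: Week 24 means of −80% and −15% before flooring at −100%, SDs of 35 and 45, within-woman correlation 0.6, and 50% to 90% of the blood returned when return is partial. The true difference is 54.1 points.

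| Partial return among bleeding women | Difference, row kept | Bias, row kept | Bias, own-visit prediction | Removed by fix |
|---|---|---|---|---|
| 10% | 56.2 | +2.1 | +0.9 | 1.2 |
| 20% | 58.6 | +4.5 | +1.8 | 2.7 |
| 30% | 60.9 | +6.8 | +2.7 | 4.1 |

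In the affected cell, 91% to 94% of relugolix and 0% of placebo women were called responders, against about 75% and 50% in truth. Repeating the exercise with a different assumed Baseline distribution gave about +2, +4 and +6.5 with the row kept, and about +1, +1.7 and +2.8 with own-visit prediction.

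**The case against.** The strongest reply is that the natural reading already treats these volumes as missing. Section 7.3.6 first identifies missing volumes through the handling rules and then speaks of imputing them. Its heading includes partially missing volumes, and Sensitivity Analysis 6 imputes the same ones. Predicting for all rows may describe only the output dataset, and the code is labelled as illustrative. This stands to the extent that a reader may not infer that the SAP puts the partial volume into the fit. It is silent, with wording that points both ways.

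A reader might also blame the missing RANDOM statement for arm-mean predictions. The algebra does not support that: with an unstructured matrix by patient, a row set to missing is predicted from her own visits. The random-effects wording is a mismatch to tidy, not the cause.

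It is fair, too, that Sensitivity Analysis 2 scores this cell on the observed volume and Sensitivity Analysis 6 multiply imputes it. Both would expose a problem, but neither corrects the primary estimate.

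Finally, all the magnitudes rest on assumed inputs, with a simulated true difference of 54.1 points against the planned 30. Part of the bias also remains after the fix, and treatment stays in the model, so arm still influences the imputed value.

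**Conclusion.** The point holds as an under-specified primary imputation rule with a directional consequence under one permitted reading. Section 7.3.6 should not leave open whether a partial Week 24/EOT volume is a response or a missing value. If it is a response, the predicted percent change is a mean for arm, visit and strata, and responder status in the FPRR < 100% cell is largely settled by arm and Baseline.

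Inflation of the primary difference requires a mean reduction below 50% on placebo and well above it on relugolix + E2/NETA. The SAP reports neither mean, so this is an assumption. Under the inputs above the bias is about +2 to +7 points for 10% to 30% partial return, of which the fix removes roughly 1 to 4. These figures are not an estimate for this trial, and the documents do not support saying that women will in fact be given their arm mean.

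**What to change.** In Section 7.3.6:

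1. State that every Week 24/EOT volume that Table 7 sends to imputation is set to missing before the model is fitted. The simulated trial in step 5 set all partial Week 24 values to missing, so also state how partial volumes that Table 7 scores directly as non-response enter the fit.
2. State that the imputed value is the patient-level prediction conditional on her own other visits, not the fixed-effect mean.
3. Align the random-effects wording with the REPEATED unstructured code.
4. As a secondary matter, state the imputation model for Group B. The code's treatment variable covers only relugolix + E2/NETA and placebo, while Sections 7.2 and 7.4 have Group B tested against placebo on this endpoint.

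The cost is a few lines of text and code. The downside is that the estimated difference may become slightly smaller.

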2.2. Sample Size Considerations

2.2.1. Sample Size Justifications for Primary Efficacy Endpoint

The following assumptions were used to determine the sample size for this study:

- 2-sided type I error rate: 0.05
- Randomization: 1:1:1
- Responder rate for placebo group: 25%
- Difference in responder rates between the relugolix + E2/NETA group and the placebo group: 30%
- Dropout rate: ~20%

With the assumption of a dropout rate of 20%, approximately 130 women in the relugolix + E2/NETA group and 130 women in the placebo group will provide at least 99% power at a 2-sided 0.05 significance level to detect a 30% difference in responder rates between relugolix + E2/NETA group and the placebo group for the primary endpoint. With an additional 130 women in the relugolix + delayed E2/NETA group, the total sample size will be approximately 390 women.

The assumed responder rate of 25% for the placebo group is within the range of responder rates observed from similar phase 3 trials in uterine fibroids (Stewart, 2017). The sample size and power calculations are based on a chi-squared test.

2.2.2. Sample Size Justifications for Percent Change in Bone Mineral Density at 12 Weeks

A pooled analysis of the percent change in BMD at 12 weeks using data from both phase 3 studies is described separately in the statistical analysis plan for the Integrated Summary of Safety. The results of this pooled analysis comparing the relugolix + E2/NETA group with the relugolix + delayed E2/NETA group will be presented in the Integrated Summary of Safety and will not be included in the CSRs for these studies.

For the comparison of the relugolix + E2/NETA group with the relugolix + delayed E2/NETA group with respect to the percent change in BMD from Baseline to Week 12 at the lumbar spine (L1–L4), approximately 260 women in the relugolix + E2/NETA group (pooled between the LIBERTY 1 and LIBERTY 2 studies) and 260 women in the relugolix + delayed E2/NETA (pooled) will provide at least 90% power at a 2-sided 0.05 significance level to detect a 1.25% absolute treatment difference, assuming a standard deviation of 4% and up to 15% dropout rate for each treatment group. Power calculations for this BMD comparison are based on a two-sample t-test.

Sample size and power calculations were performed using the software package *nQuery* 4.0 (Statistical Solutions Ltd.).

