7.3.1. Primary Efficacy Analysis

The following primary hypothesis for the primary efficacy endpoint will be tested:

Null hypothesis $H_0: \pi_R \leq \pi_P$ versus Alternative hypothesis $H_{a1}: \pi_R > \pi_P$

where π_R and π_P are the responder rates at Week 24/EOT for relugolix + E2/NETA (Group A) and placebo (Group C), respectively.

The treatment comparison between the relugolix + E2/NETA and the placebo will be analyzed using a Cochran-Mantel-Haenszel test statistic for proportions stratified by the Baseline mean MBL volume using the alkaline hematin method (< 225 mL versus ≥ 225 mL) and geographic region (North America versus Rest of World). The difference in responder rates between the relugolix + E2/NETA and placebo and its two-sided 95% CI will be estimated using stratum-adjusted Mantel-Haenszel proportions. The unadjusted responder rates and the difference in responder rates between the relugolix + E2/NETA and placebo groups and the corresponding two-sided 95% CI also will be provided. The study will be considered positive if the treatment effect for the primary endpoint is statistically significant with two-sided p-value < 0.05 .

[figure not shown]
For the primary analysis, primary endpoint will incorporate the missing data handling rules described in Section [7.3.5](#).

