- If the reason is Other and the specification describes spotting or negligible bleeding, responder status will be defined as follows:

- The patient will be considered as a responder if it is supported by the eDiary data: the eDiary entry rate must exceed 70% and the patient must have reported no more than 5 total days of bleeding with product use and no more than 3 consecutive bleeding with product use over the collection interval.
- If the eDiary entries did not confirm spotting or negligible bleeding, but the patient had at least 8 weeks of MBL volume data prior to the Week 24/EOT visit, her missing MBL volume will be imputed to determine responder status. Eight weeks of MBL volume data represents a reasonable minimum length of observation to justify imputation of the remaining data in assessing the effects of hormonal therapy.
- Otherwise if the patient had < 8 weeks of MBL volume data, she will be considered as a non-responder;

- If the reason is any Other, the responder status will be derived as follows:

- If the patient had at least 8 weeks of MBL volume data prior to the Week 24/EOT visit, her missing MBL volume will be imputed and her responder status will be based on the imputed MBL volume.
- If the patient had < 8 weeks of MBL volume data, she will be considered as a non-responder.

Table 7: Derivation of Responder Status at Week 24/EOT and Missing Data Handling Rules – for Primary Analysis

Treatment Exposure	FP Collection (FPRR)	Observed MBL Volume	Reason for No FP Collection	Responder Status
< 4 weeks	N/A	N/A	N/A	Imputed as non-responder
≥ 4 weeks	100% FP Compliance	N/A	N/A	Based on the observed MBL volume
	<100% FP Compliance	MBL volume ≥ 80 mL or <50% reduction from Baseline	N/A	Imputed as non-responder based on the observed MBL volume
		MBL volume < 80 mL and ≥ 50% reduction from Baseline	N/A	Based on the imputed MBL volume
	No FP Collection	N/A	Reported “Amenorrhea”	Imputed as responder
			Reported “Spotting or negligible bleeding” and confirmed by eDiary ^a	Imputed as responder
			Reported “Spotting or negligible bleeding” although not confirmed by eDiary or any other reason, had at least 8 weeks of MBL volume data	Based on the imputed MBL volume
			The entries in the eDiary did not verify “Spotting or negligible bleeding” or any other reason and if had < 8 weeks of MBL volume data	Imputed as non-responders

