Normalizing transformations will be applied to the statistics estimated from each imputed dataset before the Rubin's combination rules can be applied (Ratitch, 2013). This combined estimation and statistical test will account for the additional variability due to imputation to provide a robust assessment of the treatment effect.

- Step 1: Identifying patients with missing or incomplete MBL volume from the longitudinal MBL volume dataset as collected.
- Step 2: Generating a monotone missing pattern using the Markov Chain Monte Carlo technique by imputing missing MBL volume measurements that are between non-missing results.

Step 3: Imputing the remaining missing values $m = 100$ times using a regression model; therefore, generating 100 complete longitudinal MBL volume datasets.

Note: if a patient missed Week 8 and prematurely discontinued study drug (eg, at Week 20) and MBL volume at Week 20 is missing or partially missing, MBL volume will be imputed for intermittent missing data at Week 8, Week 20 (EOT), and Week 24 due to discontinuation.

Step 4: Performing the same CMH test pre-specified for the primary endpoint analysis and estimating the responder rates for each arm using each of the 100 datasets based upon the MBL volume at Week 24/EOT.

Note: in the example above, the imputed MBL volume at Week 20 (EOT) will be used in the analysis, although MBL volume is imputed at Week 24.

Step 5: Combining the results from the 100 complete datasets to make inferences about the treatment effect on the responder rate.

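### The primary analysis treats a single thresholded mixed-model prediction as an observed response, so its p-value and confidence interval leave out imputation uncertainty

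*SAP*

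**What the plan says.** Section 7.3.5 and Table 7 send two kinds of women to the imputation model:

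- **Incomplete return.** Those with a product return rate below 100% whose returned volume already meets both responder criteria "will be imputed for partial or complete missing MBL volume".
- **No collection.** Those with at least 8 weeks of earlier MBL data, where the reason is neither reported amenorrhea nor diary-confirmed spotting, have status "based on the imputed MBL volume". A report of amenorrhea over an interval shorter than 35 days that cannot be confirmed is also imputed.

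Section 7.3.6 fits one REML repeated-measures model for percent change in MBL. It contains treatment, visit, their interaction, the two stratification factors and patient-level random effects, with an unstructured within-patient covariance. One predicted percent change per woman and visit is converted to mL, and "the predicted MBL volumes at the corresponding Week 24/EOT visit will be used to determine responder status".

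Section 7.3.1 applies the stratified Cochran-Mantel-Haenszel test to that status. For the difference, "its two-sided 95% CI will be estimated using stratum-adjusted Mantel-Haenszel proportions". It adds: "The study will be considered positive if the treatment effect for the primary endpoint is statistically significant".

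Multiple imputation (by arm, m = 100, Rubin's rules) appears only in section 7.3.7.6, as Sensitivity Analysis 6. Of that analysis the SAP says: "This combined estimation and statistical test will account for the additional variability due to imputation". It makes no such statement about the primary analysis.

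**The concern.** A predicted value is an estimate of a conditional mean. Cutting it at 80 mL and 50% turns an uncertain outcome into a certain 0 or 1, and sections 7.3.1 and 7.3.6 contain nothing that puts the uncertainty back. This has two consequences:

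- The reported variance is too small, so the interval is too narrow and the p-value too optimistic.
- Each imputed woman is moved to her likelier status, which can bias the responder difference either way, depending on the true rates.

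The primary p-value alone decides whether the study is positive and opens the gate to the seven alpha-protected secondary endpoints (section 7.4.1). The primary interval is the main statement of effect size.

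**Working it through.** **1. The plan's own figure.** Section 2.2.1 gives "2-sided type I error rate: 0.05", 25% versus 55%, 130 women per arm and about 20% dropout, hence 130 × 0.8 = 104 evaluable per arm.

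- SE under the null = √(2 × 0.40 × 0.60 / 104) = 0.0679
- SE under the alternative = √((0.25 × 0.75 + 0.55 × 0.45) / 104) = 0.0647
- z = (0.30 − 1.96 × 0.0679) / 0.0647 = 2.58, so power is 99.5% (99.9% with 130 per arm)

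The stated power of at least 99% reproduces and is not in question.

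**2. What thresholding does.** For baseline volume B, a woman responds if her percent change is at most −50 and also below 100 × (80/B − 1). The two limits coincide at B = 160 mL, so each woman has one cut-off. Let p be her probability of falling below it given her history. With roughly symmetric residuals, the prediction scores her 1 if p > 0.5 and 0 otherwise.

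- Her expected contribution moves from p to 1 or to 0.
- Her conditional variance p(1 − p) is replaced by 0.

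Rubin's total variance is T = Ū + (1 + 1/m)B_m, where Ū is the average within-imputation variance and B_m the between-imputation variance. Section 7.3.1 uses only an ordinary binomial-type variance and has no B_m term. If the prediction were instead read as a stratum, arm and visit mean, it would still be one deterministic value.

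**3. Size.** The SAP gives no imputed share, so shares are assumed; the 20% in section 2.2.1 is dropout, not imputation. The other assumptions are:

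- 130 per arm, six visits and four strata
- percent-change SD 45, floored at −100
- between-visit correlation 0.3 to 0.7 (compound symmetry)
- baseline lognormal, median 190 mL, log-SD 0.5, at least 80 mL
- arm means calibrated to the stated responder rates, 5,000 runs per cell, Monte Carlo error about 0.3 points

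Ranges below run over the correlations. Coverage and bias are at 55% versus 25%; type I error is at 25% in both arms.

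| Missingness | Imputed | 95% CI coverage | Bias (points) | Type I error |
|---|---|---|---|---|
| Complete data | 0% | 93.6-94.8% | – | 4.3-5.7% |
| Table 7 selection | 3.8% | 93.5-95.1% | +0.1 to +0.3 | 4.8-5.3% |
| Table 7 selection | 7.6% | 92.3-93.4% | +0.3 to +1.0 | 5.4-6.3% |
| Table 7 selection | 15.3% | 88.5-92.9% | +0.8 to +2.0 | 5.8-6.8% |
| Completely at random | 5% | 93.3-94.5% | +0.1 to +0.7 | 4.9-5.8% |
| Completely at random | 10% | 91.3-93.2% | +0.3 to +1.4 | 4.8-6.3% |
| Completely at random | 20% | 85.5-91.4% | +0.9 to +2.6 | 6.5-7.8% |

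In the Table 7 rows, 5%, 10% or 20% of women were flagged, half with no collection and half returning 50-95% of their true volume. Incomplete returners were imputed only if the returned volume met both criteria.

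- **Standard error.** With 20% missing at random, the mean reported SE was 5.49-5.60 points against an actual SD of 6.15-6.73. That is 1 − 5.60/6.15 = 9% to 1 − 5.49/6.73 = 18% too small (2-3% with complete data).
- **Direction of bias.** At 40% versus 10% with 20% imputed, bias was −0.5 to +0.2 points and coverage 89.8-93.5%.
- **Power** at 55% versus 25% stayed at or above 99.6%.

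**4. Cross-checks.** A second simulation used percent-change SD 28-30, correlation 0.3 and 0.6, random missingness and a true difference of about 0.31. With 20% imputed:

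- coverage was 86.5% and 93.3%
- type I error was 8.5% and 6.3%, against 4.8-5.4% with full data
- the single-prediction SE was 0.0554-0.0561 against 0.0606-0.0619 under multiple imputation, or 7-10% too small

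A further simulation with Table 7 selection and about 15% imputed gave coverage 88.5-92.5%, reported SE 0.055-0.056 against an actual SD of 0.060-0.065, bias +0.7 to +2.0 points and type I error 6.0-6.6%.

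**The case against.** The strongest counter-case concerns size.

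- **Imputed share.** Table 7 settles many women without the model: under 4 weeks of treatment, reported amenorrhea, diary-confirmed spotting, under 8 weeks of data with no collection, and incomplete returns that already fail a criterion. A dropout with an end-of-treatment collection is not imputed either. Nothing in the SAP shows that 15-20% would be imputed, and at 5% the results are barely distinguishable from complete data. This stands, which is why the size is stated by share. The pool is not trivially small by design, however: any apparent responder with a return rate below 100%, even by one day, goes to the model.
- **Width versus bias.** Part of the lost coverage is bias rather than narrowness. This also stands, but both come from the same step.
- **Decision.** With the planned effect, the primary decision would probably not change. Agreed; but error control and coverage must hold whatever the true effect.
- **Sensitivity analyses.** Analyses 2 and 6 would expose a discrepancy. They would not correct the p-value on which section 7.3.1 judges the study, and the SAP does not say what follows if they disagree.
- **Remedy.** Sensitivity Analysis 6 as written has a bias of its own, shown with the fix.

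**Conclusion.** The concern holds. From the text it is certain that the primary p-value and interval contain no allowance for imputation; the size of the effect is not certain. Under the stated assumptions it is negligible at about 4-5% imputed, small up to about 10%, and clear at about 15-20%, where coverage falls to roughly 86-93% and type I error rises to roughly 6-8%. The bias is mostly an overstatement at 55% versus 25%, but its sign is not fixed. The results rest on the assumed share, SD, correlation structure and baseline distribution. The sample size justification is untouched. This should be corrected, but it does not by itself overturn the design.

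**What to change.** In sections 7.3.1 and 7.3.6, make multiple imputation with Rubin's rules the primary handling of the Table 7 cells that rely on an imputed volume. Apply the responder criteria within each completed dataset, then combine the Cochran-Mantel-Haenszel test and the Mantel-Haenszel difference. There are two routes:

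- **Draw from the mixed model's patient-level predictive distribution for percent change**, with both parameter and residual draws. In simulation this gave 94.4-95.5% coverage and a bias of −0.3 to −0.8 points.
- **Promote Sensitivity Analysis 6 as written** (by arm, m = 100). At correlation 0.5 with 2,000 runs, coverage was 95.2-96.0% and type I error 3.5-4.2%. The standard error was about 2-11% larger than the single-prediction one. Its normal draws on the volume scale pull the difference down by 0.3 to 1.8 points.

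The first route keeps the SAP's own model and shows less bias. Under either, move the single prediction to a sensitivity analysis and report the number of women imputed by arm and by Table 7 row. The cost is SAP wording before unblinding. The multiple-imputation program is already planned, and the somewhat wider interval reflects uncertainty that is really there.
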